**Secondary Endpoint #3:** Progression-Free Survival (PFS) – Comparison between subjects randomized to DCVax®-L and those randomized to Placebo within Study 020221.

PFS as described in the original trial protocol uses modified Macdonald criteria to define disease progression and compares PFS between subjects randomized to DCVax®-L to those randomized to placebo within the Trial. The MacDonald criteria are no longer used in the field and cannot distinguish between actual disease progression and pseudoprogression. This endpoint will therefore likely be confounded due to pseudo-progression (PsPD) events being counted as PD. Such PsPD may be due to effects of surgery and/or radiation therapy or may also be induced by the DCVax®-L vaccine (i.e., T cell infiltration). This second form of PsPD occurs frequently in subjects receiving DCVax®-L, as may be seen through case studies.

**Secondary Endpoint #4:** Overall Survival (OS) – Comparison between subjects randomized to DCVax®-L and those randomized to Placebo within Study 020221.

OS as described in the original trial protocol compares survival in subjects randomized to DCVax®-L to those randomized to placebo within the Trial. Secondary Endpoint #4 is an OS analysis on this basis. However, due to the crossover option in the trial design for all patients in both arms of the Trial, and the fact that 90% of the total patients have received DCVax®-L, this means that the majority of subjects randomized to placebo have received DCVax®-L treatment following disease progression. This will result in a potential convergence of the survival curves if there is a survival benefit conferred on these crossover subjects as a result of the DCVax®-L treatment.

**Secondary Endpoint #5:** Tumor Response – Comparison between subjects randomized to DCVax®-L and those randomized to Placebo within Study 020221.

Resection of GBM typically focuses on removing the enhancing tissue as that is supposed to be the area of active tumor growth. Incomplete resections result in residual enhancing disease post-surgery and most patients also have non-enhancing disease areas surrounding the enhancing lesion. Tumor response will use pre- and post-randomization measurements of enhancing and non-enhancing disease. Modified RANO criteria will be applied per Cloughesy et al. [7], allowing for evaluation of non-measurable disease to determine response rates.

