#### 8.3.2 Analysis for OS, PFS

The intent of the original protocol was that the Cox proportional hazards model will be used for the primary analysis of OS. However the OS endpoint analysis may be confounded by non-proportional hazards due to the effects of the crossover option that was built into the protocol from the outset. Under this crossover option, all subjects from both arms of the Trial were allowed to opt to receive the active treatment DCVax®-L at the time of disease progression (measured by MRI), while remaining blinded to their initial treatment assignment. If subjects originally assigned to placebo receive treatment benefit in terms of extended survival as a result of this crossover option, then we can expect the survival curves to converge. To address possible non-proportionality while controlling type I error, a testing procedure based on a weighted log-rank statistic that was developed by Karrison will be used [28].

The intent of the original protocol was that the Cox proportional hazards model will be used for the primary analysis of PFS. When the protocol was developed in 2006 the phenomenon of pseudo-progression was largely unknown. Since then, pseudo-progression has become well recognised as a

major issue. It is now expected that, because early events specifically may not represent true disease progression, differentially in the two randomized groups, the proportional hazards assumption may not hold; the hazard ratio is expected to decrease with time as the effect of PsPD decreases.

For OS and PFS, Karrison's approach to the weighted log rank test will be used [28], based on the ITT population. A one-sided p value will be presented.

Along with the p value for the test, the hazard ratio, with a 95% confidence interval, will be presented. Estimates of 6, 12, 18, 24, 30, 36, 42, 48, 54 and 60 month OS and PFS will be provided, with 95% confidence intervals, for both randomized treatment groups.

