#### 1. OS, PFS and cPFS: Cox model (ITT)

A Cox proportional hazards regression model [29] based on the ITT population will be used. The following baseline covariates will be assessed (one at a time) for their additional contribution to the statistical model, and each covariate showing a significant (P < 0.05) contribution will be included in the final model, for each endpoint separately. Subjects with missing data in the continuous variables (age, KPS) will be excluded from the respective analysis. Hazard ratios, estimates of survival to 6, 12, 18, 24, 30, 36, 42, 48, 54 and 60 months and 95% confidence intervals will be provided.

- Sex: Male / female
- Age at randomization: years
- MGMT status at randomization: Yes, No, unknown
- Karnofsky Performance Status at randomization: score
- Extent of resection: Complete, partial (or incomplete), unknown
- Absolute lymphocyte count at randomization: ≤ 1,000 /μL, > 1,000/μL, unknown

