Visit 2 (Post-surgery MRI): MRI scans pre- and post-surgery need to document extent of resection beyond biopsy only. Patients must have a surgically accessible tumor for which surgical resection, with intent to perform a gross total or near gross total resection, is indicated. Biopsy only does not satisfy eligibility rules. MRI scan (post-surgical) must demonstrate that a resection was performed beyond biopsy only. All MRI scans will be reviewed by central independent radiology review.

The post-surgery MRI will be used to quantitatively determine the extent of resection for purposes of the statistical analyses in section 13.2.3 and 13.3.3. Extent of resection will be defined as the amount of residual tumor volume measured in mm^3.

The amount of tumor lysate protein is determined as soon as possible after surgery by the contract manufacturer. Determination that sufficient tumor lysate protein was generated is required for a patient to remain eligible and to undergo leukapheresis.

<sup>4 Hegi, ME et al. 2005. N Engl J Med. 2005 Mar 10;352(10):997-1003.

Patients may have received steroid therapy as part of their primary treatment. Steroid treatment should preferably be stopped, but if continued steroid use is clinically indicated, be tapered down to the lowest acceptable dose (i.e. no more than 4 mg dexamethasone qd) approximately 7 days prior to leukapheresis to secure the highest possible quality of the cells used for DCVax-L manufacturing.

Visit 3 (Pre-leukapheresis): Just prior to proceeding to leukapheresis, patients are assessed for viral status and bone marrow and liver function. The following tests and procedures are done at the pre-leukapheresis visit:

- Sign study Informed Consent Form (second Informed Consent)
- History
- Pregnancy test
- Hematology: CBC, differential, platelets
- Virology testing: HIV-1, 2, HTLV-1,2, Hepatitis B, C
- Serum Chemistries: calcium, SGOT, SGPT, alkaline phosphatase, LDH, total bilirubin, BUN, creatinine, electrolytes, magnesium and glucose
- Urinalysis: normal routine urinalysis

Collection of AE and concomitant medications begins at Visit 3.

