#### 13.2. PRIMARY ENDPOINT, HYPOTHESIS, AND ANALYTIC METHOD

- 13.2.1. Endpoint: Time to objective demonstration of disease progression or death, measured from time of randomization, (PFS)
- 13.2.2. HYPOTHESIS: PFS, measured form time of randomization, will be longer on average for patients in the investigational arm, who were treated with DCVax-Brain compared to placebo.
- 13.2.3. ANALYTIC METHOD: Proportional hazards (Cox) regression. The effect of DCVax-Brain will be tested in a model with the treatment group, age, extent of resection, and KPS as covariates, since age, extent of resection (expressed as residual tumor volume after resection), and KPS are considered possibly related to PFS. The effect of treatment should be significant (two-sided p-value for coefficient of treatment group ≤ 0.05) to support a conclusion of a significant effect of DCVax-Brain on PFS.

Randomization into the investigational arm of the study takes place after patient eligibility has been confirmed through tests performed at the Baseline Visit.

The analysis will be an intent-to-treat analysis; that is, all randomized patients who contribute any follow-up data for PFS will be included.

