#### 13.3. SECONDARY ENDPOINT, HYPOTHESIS, AND ANALYTIC METHOD

- 13.3.1. ENDPOINT: Time to death (OS)
- 13.3.2. HYPOTHESIS: Survival, measured from time of randomization, will be longer on average for patients in the investigational arm who were treated with DCVax-Brain compared to placebo.
- 13.3.3. ANALYTIC METHOD: Cox regression. All randomized patients who contribute any follow-up data for survival will be included in the analysis. The effect of DCVax-Brain will be tested in a model with treatment group, age, extent of resection (expressed as residual tumor volume after resection), and KPS as covariates. The effect of treatment should be significant (two-sided p-value for coefficient of treatment group ≤ 0.05) to support a conclusion of a significant effect of DCVax-Brain on OS. Randomization takes place after patient eligibility has been confirmed through tests performed at the Baseline Visit.

The analysis will be an intent-to-treat analysis; that is, all randomized patients who contribute any follow-up data for OS will be included.

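### The randomised comparisons of cPFS, PFS and OS name no baseline covariates or strata, and the SAP does not say that protocol v4.0's covariates were dropped

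*Combined protocol and SAP*

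**What the plan says.** SAP 1.2.3 introduces Secondary Endpoint #4 with: "OS as described in the original trial protocol compares survival in subjects randomized to DCVax®-L to those randomized to placebo within the Trial". SAP 8.3.2 gives the test: "For OS and PFS, Karrison's approach to the weighted log rank test will be used [28], based on the ITT population". It promises a hazard ratio with a 95% interval but no model for it, and it names no covariate or stratum. SAP 8.3.3 assigns cPFS to a Cox model in one sentence, again without covariates.

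Covariates for these endpoints appear only in 8.3.4, under exploratory analyses. There they are tried one at a time, and "each covariate showing a significant (P < 0.05) contribution will be included in the final model, for each endpoint separately". Extent of resection is coded complete, partial or unknown. Table 2 lists Cox models for OS and PFS as sensitivity analyses, also without covariates.

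Protocol v4.0 was more specific. For PFS (13.2.3): "The effect of DCVax-Brain will be tested in a model with the treatment group, age, extent of resection, and KPS as covariates". For OS (13.3.3) the treatment effect was to be "tested in a model with treatment group, age, extent of resection (expressed as residual tumor volume after resection), and KPS as covariates". Success was judged on that model ("two-sided p-value for coefficient of treatment group ≤ 0.05"). The summary of changes records absolute lymphocyte count as an added covariate at v6.0. Protocol v7.0, section 8.2, still says: "The post-surgery MRI will be used to quantitatively determine the extent of resection for purposes of the statistical analyses in section 13.2.3 and 13.3.3". In v7.0, section 13 covers adverse events and has no such subsections.

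**The concern.** SAP Section 6 calls age, extent of resection and performance status known prognostic factors. Leaving strong prognostic factors out of a survival comparison lowers its power. Secondary #2 to #4 are the only randomised comparisons in the Table 2 testing order; everything above them uses external controls. The SAP is also uneven within itself: it fixes a covariate list for immunostimulatory response (8.4.1) and stratifies the KPS-change test by MGMT (8.4.2), both exploratory, but does neither for the gatekept endpoints.

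With the model behind the PFS and OS hazard ratios unstated, the choice between an adjusted and an unadjusted ratio could be made after unblinding.

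**Working it through.** **1. Inputs from the documents.** ITT population 331 (SAP Section 1), of whom 232 were randomised to DCVax-L (1.2.1), leaving 331 − 232 = 99 controls. OS planning (1.3.2): medians 17 and 25.3 months, HR 17/25.3 = 0.672, one-sided 0.025, 233 events, 80.5% power. PFS planning (1.3.1): medians 7 and 11 months, HR 7/11 = 0.636, one-sided 0.01, 248 events, 84% power. Allocation 2:1. Secondary endpoints are tested at 2.409% (8.3.1), one-sided by the footnote to Table 2.

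**2. The plan's own figures.** Schoenfeld: D = (z_α + z_β)² / [p₁p₂(ln HR)²], with p₁p₂ = 1/3 × 2/3 = 0.2222.
- OS: (1.960 + 0.860)² / (0.2222 × 0.1581) gives 227 events (stated 233); 233 events give 81.6% power (stated 80.5%).
- PFS: (2.326 + 0.994)² / (0.2222 × 0.2043) gives 243 events (stated 248); 248 events give 84.8% (stated 84%).

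The plan's figures reproduce closely, and they are for an unadjusted log-rank test.

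**3. Assumption.** The documents do not give the prognostic strength of the covariates. It is represented by the SD of their combined log-hazard score, over a range. The planning HR is taken as the covariate-conditional HR.

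**4. Cox tests, unadjusted against adjusted.** 3,000 simulated trials per setting, 232:116, exponential times, uniform 36-month accrual, analysis at 233 deaths or 248 PFS events, three normal covariates, planning alphas.

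| Score SD | OS power, unadjusted / adjusted | Mean OS HR, unadjusted / adjusted | PFS power, unadjusted / adjusted |
|---|---|---|---|
| 0 | 82.9% / 82.9% | 0.67 / 0.67 | 86.6% / 86.5% |
| 0.3 | 79.1% / 82.4% | 0.68 / 0.67 | 81.9% / 85.9% |
| 0.5 | 73.9% / 83.7% | 0.70 / 0.67 | 75.3% / 85.8% |
| 0.7 | 67.6% / 83.0% | 0.72 / 0.67 | 67.3% / 86.0% |

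OS differences at SD 0.3, 0.5 and 0.7: 82.4 − 79.1 = 3.3, 83.7 − 73.9 = 9.8 and 83.0 − 67.6 = 15.4 points.

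A second run used the actual 232:99 and one-sided 2.409% (1,500 trials per setting, SD 0.30 / 0.45 / 0.60). OS power was 71.9% / 69.9% / 65.2% unadjusted against 76.3% / 76.5% / 77.3% adjusted, a loss of 4 to 12 points.

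**5. The test the SAP actually names.** A Karrison-type test (maximum of three weighted log-ranks), 232:99, one-sided 2.409%, 2,000 trials, proportional hazards, SD 0.30 / 0.45 / 0.60, unstratified against four coarse age/KPS and resection strata.
- OS: 72% / 67% / 61% against 73% / 69% / 66%, a gain of 1, 2 and 5 points.
- PFS: 87% / 84% / 78% against 88% / 87% / 84%, a gain of 1, 3 and 6 points.

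**6. Null check.** At SD 0.7 with no effect (OS, nominal 2.5%), unadjusted and adjusted Cox tests rejected in 3.1% and 3.3% of trials (Monte Carlo SE about 0.3 points). Both are slightly above nominal, but alike. The Karrison-type test rejected in 2.6% to 3.5%, similarly with and without strata.

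None of these runs models crossover or non-proportional hazards.

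**The case against.** The strongest reply is that the SAP misdescribes nothing. The sentence in 1.2.3 says which arms are compared, in contrast with the external-control primary endpoint; it makes no claim about the model. Section 8.3.2 openly says the original intent was Cox and gives reasons for leaving it: crossover and pseudo-progression. That stands, so a reader who infers a misstatement about the original protocol goes too far. But those reasons concern proportionality. They do not explain losing the covariates, because a weighted log-rank test can be stratified and cPFS stays in a Cox model.

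A reader might also infer that a model fixed in 2007 was abandoned. The documents do not show that. v6.0 added a covariate; the statistical text between v4.0 and v7.0 is not supplied; v7.0 section 16 defers to the SAP. SAP 1.4 even attributes to the original protocol two PFS interim analyses, at 149 and 198 events, that differ from v4.0's single conditional-power look. The last covariate model before the SAP cannot be seen.

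The P<0.05 screen cannot alter any gatekept test, since it sits only in exploratory models, and v4.0 (13.7) itself planned covariate modelling as a secondary analysis. Residual tumour size survives as a planned subgroup factor (Tables 5 and 8). cPFS is a new endpoint with no earlier model, so the case for adjusting it rests on the SAP's own list of prognostic factors.

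**Conclusion.** The point holds as a gap in specification with an avoidable loss of power. The gatekept within-trial analyses name no covariates or strata, the model for the reported PFS and OS hazard ratios is open, and the SAP does not say that covariates specified in v4.0 were dropped.

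The size cannot be derived from the documents. Under the assumed score SD of 0.3 to 0.7, Cox tests of OS lose about 3 to 15 points relative to an adjusted analysis, under proportional hazards and without crossover. For Karrison's test, coarse stratification recovers only about 1 to 6 points at SD 0.30 to 0.60, so the Cox figures should not be read as the gain available for the PFS and OS tests.

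Three further inferences are unsupported. The planned 80.5% and 84% are not undercut if the planning medians are marginal, because they were computed for an unadjusted log-rank test. Type I error is not inflated by omitting the covariates. The shift in the hazard ratio from 0.67 towards 0.68 to 0.72 is non-collapsibility, the difference between a conditional and a marginal ratio, and not bias.

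**What to change.** 1. SAP 8.3.3: test cPFS in a Cox model with fixed covariates: age, KPS, residual tumour volume (or resection category), absolute lymphocyte count and MGMT status, a randomisation stratum (1.5).
2. SAP 8.3.2: take the reported PFS and OS hazard ratios and 95% intervals from the same fixed model. Stratify Karrison's test by MGMT and, if cells allow, by RPA class (as defined under Table 5) or resection.
3. SAP 8.3.4: replace the one-at-a-time P<0.05 screen with this fixed model as a named sensitivity analysis, in line with Table 2.
4. State in 8.3.2 that the test departs from the covariate-adjusted Cox model of v4.0, and correct the reference to 13.2.3 and 13.3.3 in protocol v7.0, section 8.2.

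The cost is wording and programming; the SAP precedes data lock and the variables are already planned for collection. Two cautions apply. Missing covariates need an unknown category or a simple baseline imputation, with a matching exception in SAP 4.2, so that no randomised patient is dropped. With 99 controls the strata must be few, so site, the other randomisation stratum with about 90 planned centres, is not a practical choice. The gain from MGMT stratification itself was not simulated.

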#### 1.2.4 Exploratory endpoints

The following exploratory (tertiary) endpoints were defined in the original clinical trial protocol:

- To compare the following between subjects in the DCVax®-L arm and subjects in the placebo arm within the Trial:
- Immune profiles in the peripheral blood that may be predictive of response/non-response to immunotherapies
- Decline in physical functioning, measured by Karnofsky Performance Status (KPS) evaluation
- Time to progression of disease (TTP)
- Survival at 6, 12, 18, 24, 30, 36, 42, 48, 54 and 60 months
- Times to PFS, OS and TTP, measured from initial surgery.
- To evaluate further the safety profile of DCVax®-L.

#### 1.3 Sample size

#### 1.3.1 Sample size for PFS

The sample size calculations were based on PFS. Table 1 shows the assumptions made.

Table 1: Assumptions Made to Support Sample Size Calculation

Ratio between the treatment arm and the placebo arm	2:1
Accrual period	36 months
Time to accrual of 50% of subjects	22 months
Follow up period	5 months
Loss to follow up, per arm per month	1%
Median PFS for placebo arm	7 months
Test for comparing PFS between arms	Log rank
Type I error	$\alpha$ = 0.01, one sided

To achieve 84% power when median PFS is 11 months in DCVax®-L-treated subjects, 348 subjects would be required in total: 232 in the DCVax®-L arm and 116 in the placebo arm. The corresponding total number of events required is 248.

#### 1.3.2 Sample size for OS

The implication of this sample size of 348, accrued as described above, for the OS endpoint is as follows. We assumed median OS of 17 months among subjects in the placebo arm, and set the type I error rate for this analysis to 0.025, one-sided. To detect the expected benefit of 8.3 months' increase in median OS (to a median of 25.3 months) in the DCVax®-L arm would require an extension of the follow up time to 36 months after completion of enrolment. Then the power of the log-rank test is approximately 80.5%. The corresponding number of events is approximately 233.

#### 1.5 Randomization

Randomization was performed using an interactive web response system (IWRS) and was initiated upon a randomization request form submitted by the trial site followed by review of all eligibility criteria. The randomization was stratified by site and by MGMT methylation status (methylated/unmethylated), and used a permuted block design with a fixed block size.

#### 1.6 Additional subject cohorts included in the study

The subjects enrolled into the study according to the inclusion and exclusion criteria defined in the study protocol (the ITT population) will be referred to as the 'Main investigational cohort'. During the course of the study, two further cohorts outside of the ITT population were added: an 'Informational cohort' and a 'Pseudo-progression cohort'.

#### 1.6.1 Informational cohort

Subjects not eligible for randomization were offered an opportunity to participate in a separate compassionate use treatment cohort since at time of screening for enrolment and randomization,

the personalized DCVax®-L product had already been manufactured. These subjects are referred to as the "Informational Cohort" or "Information Arm" and are not part of the main study.

#### 1.6.2 Pseudo-progression cohort

A group of subjects, also not included in the 331 patients main study, who already had evidence of possible progressive disease at baseline (and hence were ineligible for the trial), but after 10 weeks' post radiation therapy did not show signs of real progression based on MRI, were assigned to the 'Pseudo-progression cohort'. Within that cohort, patients were randomized at a ratio of DCVax-L to Placebo of 2:1.

#### 1.7 Genomic/genetic outliers

New molecular and genetic information that has emerged in the field may be of relevance in interpreting the data emerging from this trial. Such data include information on IDH1 mutational status and 1p19q chromosomal deletions. Patients with these mutations are generally considered to suffer from a lower grade glioma, with extended time to progression and longer survival times. These forms of glioma had not been identified in 2007 at the time the study was initiated, and it is possible that some patients randomized into the study may have these molecular subtypes, despite the histological confirmation of GBM. Sensitivity analyses for the Trial endpoints will include analyses on patients who do not have either one of these genetic variations.

# **Section 2:** Analysis sets

#### 2.1 Study cohorts

The total study population comprises three cohorts of subjects:

- Main investigational cohort: all subjects satisfying the protocol eligibility criteria (the ITT population)
- Pseudo-progression cohort
- Informational cohort

